3.9.2 Secondary outcomes

Secondary outcomes as follows:

- Mortality within 1 year;
- Ischemic stroke outside the territory of the qualifying artery within 1 year;
- Disabling stroke within 1 year;
- TIA in the territory of the qualifying artery within 1 year;
- Unplanned revascularization (EC-IC bypass surgery or ER) of the qualifying artery within 1 year;
- Myocardial infarction within 1 year;
- Composite vascular events within 1 year;
- Quality of life assessment (EuroQol -Five-Dimensions [EQ-5D] scale questionnaire) at 1 year;
- mRS score at 1 year;
- Periprocedural outcomes;
- Restenosis or reocclusion (symptomatic or asymptomatic).

Disabling stroke is defined by any of the following: (1) an mRS score of 3 or more, (2) an increase of at least 1 point in the mRS score from prestroke baseline, (3) a score on the composite NIHSS of 7 or more, or (4) an increase of at least 4 points in the NIHSS score from pre-stroke baseline.

TIA is defined as duration of a focal or global neurological deficit <24 hours, any variable neuroimaging does not demonstrate a new hemorrhage or infarction.

Composite vascular events within 1 year included any stroke, myocardial infarction, and unplanned revascularization within 1 year.

Periprocedural outcomes are: (1) successful recanalization rate, (2) periprocedural complications: in-stent thrombosis, distal embolization, symptomatic intracranial hemorrhage, parenchymal hematoma type 2 (defined by the Heidelberg classification³⁴), arterial dissection, arterial perforation, (3) residual stenosis, (4) NIHSS score at 24-72 hours, (5) death within 7 days.

Restenosis is defined as >50% stenosis within or immediately adjacent (within 5 mm) of the treated segment and >20% absolute luminal loss, reocclusion is defined as total occlusion of the target artery segment.

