Secondary Endpoints	
Secondary outcomes as follows:
 
 • Mortality within 1 year; • Ischemic stroke outside the territory of the qualifying artery within 1 year; • Disabling stroke within 1 year; • TIA in the territory of the qualifying artery within 1 year; • Unplanned revascularization (EC-IC bypass surgery or ER) of the qualifying artery within 1 year; • Myocardial infarction within 1 year; • Composite vascular events within 1 year, including any stroke, myocardial infarction, and unplanned revascularization; • Quality of life assessment (EuroQol-5-Dimensions scale questionnaire) at 1 year; • mRS score at 1 year; • Periprocedural outcomes; • Restenosis or reocclusion (symptomatic or asymptomatic).
Statistical Methods	
 • Categorical variables will be compared between treatment groups using χ^2 or Fisher's exact test. Continuous variables or ordinal variables will be compared between treatment groups using t-test or Wilcoxon-Mann-Whitney test. • The primary and time-to-event secondary outcomes will be compared between the groups using log-rank test. • Kaplan-Meier curves will be used to show the incidence of outcomes over time. • The hazard ratio (HR) and adjusted hazard ratio (aHR) between groups, along with their 95% CIs, will be determined using univariate and multivariate Cox proportional hazards regression models. • Propensity score matching (PSM) will be performed to reduce the possible influence of selection bias and confounders on the outcomes. • A 2-sided P value less than 0.05 is considered to demonstrate a statistically significant difference. • All analyses will be performed with using SAS Version 9.4.

Schedule of assessments

Table 1: Summary of Study Treatment and Study Assessments

Study Requirements	Screening and Baseline	Endovascular recanalisation			Discharge	Follow-up Visits		
		Pre-procedure	Intra-procedure	Post-procedure		30-Day (±7 days)	90-Day (±7 days)	1-Year (±30 days)
Inclusion/Exclusion	X	X						
Informed Consent	X							
Clinical Assessment, Vital Signs, and Physical Exam	X	X			X	X	X	X
Laboratory tests	X					X	X	X
NIHSS (blinded to treatment)	X				X	X		
mRS (blinded to treatment)	X				X	X	X	X
EQ-5D (blinded to treatment)						X	X	X
mTICI assessment		X	X	X				
CT/MRI	X			X			X	X
CTP/PWI	X						X	X
CTA/DSA	X						X	X
Protocol Deviations		X	X	X	X	X	X	X
Medication review and patient compliance survey	X	X	X	X	X	X	X	X

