3.8 Follow-up

All participants will be followed up by the neurologists at 30±7 days, 90±7 days, 1 year ±30 days. The preferred follow-up modality is to implement face-to-face clinical evaluations. At every scheduled follow-up visit, the participants' medication regimens, laboratory tests, risk factor management (as previously outlined), and potential adverse clinical events/outcomes are evaluated by an experienced neurologist and/or neurointerventionalist. When patients are unable to attend on-site clinical follow-ups, a remote telephonic follow-up will be utilized as an alternative method of patient assessment. During the 1-year follow-up period, all patients are required to undergo a neurovascular imaging examination including DSA, CTA or MRA.

For perioperative patients in ER group, a clinical examination including the National Institutes of Health Stroke Scale (NIHSS) and Glasgow Coma Scale (GCS) will be carried out at 24-72 hours after the procedure. Meanwhile, patients will undergo CT to assess the cerebral hemorrhage at 24-72 hours, if possible, supplementary assessment of vessel recanalization status will be conducted through CTA or MRA. At the one-week post-intervention assessment, a clinical evaluation will be conducted, including patients' clinical status, NIHSS score, GCS score, and adverse events.

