3.11.4 Documentation of Adverse Events

All SAEs will be recorded in the case report form (CRF) table. The details of the SAEs, including start time, end time, duration, treatment, outcome, and relationship to the intervention, will also be documented. The frequency of SAEs will be summarized according to the study assignments. All recorded AEs and SAEs will be reported to the investigator. In this study, SAEs primarily refer to disabling strokes, symptomatic intracranial hemorrhages or death within 1 year after enrollment.

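### Disabling stroke has no fixed reading time, and routine early NIHSS is scheduled only in ER patients, so early strokes that recover may be coded disabling more often in that group

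*Protocol*

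**What the plan says.** **Definition.** Protocol 3.9.2 uses an any-of rule: "Disabling stroke is defined by any of the following". The mRS criteria are "1) an mRS score of 3 or more, (2) an increase of at least 1 point in the mRS score from prestroke baseline". The NIHSS criteria are "3) a score on the composite NIHSS of 7 or more, or (4) an increase of at least 4 points in the NIHSS score", the last also measured from a pre-stroke baseline. No interval after the stroke is given for any of the four.

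**Common schedule.** In Table 1 the row "NIHSS (blinded to treatment" is marked at baseline, discharge and 30 days. It is blank at 90 days, at 1 year and in the post-procedure column. The row "mRS (blinded to treatment" is marked at baseline, discharge, 30 days, 90 days and 1 year.

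**ER-only examinations.** Section 3.8 sets an examination at 24-72 hours after the procedure: "For perioperative patients in ER group, a clinical examination including the National Institutes of Health Stroke Scale (NIHSS". It then adds "At the one-week post-intervention assessment, a clinical evaluation will be conducted", again with NIHSS.

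**Data lists.** Sections 3.10.3 to 3.10.5 (30 days, 90 days, 1 year) name mRS but not NIHSS.

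**Use.** Disabling stroke within 1 year is a secondary outcome in both documents. It is also one of three named SAE types ("SAEs primarily refer to disabling strokes", Protocol 3.11.4, repeated in SAP 5.3). The SAP's safety section tests SAE incidence between the groups.

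**The concern.** Under an any-of rule, an additional examination can add a disabling label but can never remove one. The two additional NIHSS examinations fall only on ER patients, in the first week after the procedure. That is also when procedural strokes would occur, and the protocol's background names procedural risk as a safety concern.

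Take a stroke that scores NIHSS 8 at 48 hours and is back at its pre-stroke mRS by the next scheduled reading. In an ER patient shortly after the procedure, the routine examination captures the 8, and criterion (3) is met. In a medical patient the same course meets a criterion only if someone happens to record an NIHSS in the acute phase. The plan permits this but does not require it. The comparison would then mix stroke severity with time of measurement.

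**Working it through.** The plan gives no expected rate, event count or sample size for this outcome, so there is no figure to reproduce. The check has two parts.

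**1. Who has a scheduled score, and when**

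| Time | NIHSS, ER | NIHSS, medical | mRS, both groups |
|---|---|---|---|
| Baseline | yes | yes | yes |
| 24-72 h after procedure | yes (3.8; Table 1 blank) | none | none |
| One week after procedure | yes (3.8; Table 1 blank) | none | none |
| Discharge | yes | yes | yes |
| 30 days | yes (Table 1; absent from 3.10.3) | same | yes |
| 90 days | none | none | yes |
| 1 year | none | none | yes |

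This takes Table 1's discharge column to apply to both groups, because it stands outside the endovascular columns. The scheduled difference is therefore two examinations within about a week of the procedure. Before and after that week the schedules match.

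For the same stroke to get different labels, three things must hold together:
- it reaches NIHSS 7, or rises by 4, while a score is being taken;
- at the next mRS reading the score is below 3 and not even 1 point above its pre-stroke value;
- no NIHSS was recorded around the event in the medical patient.

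**2. Illustrative size, with no true treatment effect**

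All three inputs are assumptions; the documents give none of them:
- e = share of disabling-type strokes that fall in the week when only ER has scheduled NIHSS (0.2 to 0.8);
- s = share of those that meet only the NIHSS criteria (0.02 to 0.20);
- d = chance that NIHSS is recorded anyway in the medical group (0 to 1).

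ER labels all of these strokes. The medical group misses the fraction e × s × (1 − d). So the apparent RR (ER vs medical) = 1 / (1 − e × s × (1 − d)).

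- e = 0.2, s = 0.05, d = 0.5: 1 / (1 − 0.005) = 1.005
- e = 0.5, s = 0.10, d = 0.5: 1 / (1 − 0.025) = 1.026
- e = 0.5, s = 0.10, d = 0: 1 / (1 − 0.05) = 1.053
- e = 0.8, s = 0.20, d = 0.5: 1 / (1 − 0.08) = 1.087
- e = 0.8, s = 0.20, d = 0: 1 / (1 − 0.16) = 1.190, the largest value in the grid
- d = 1: 1.00 throughout

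The direction is always against ER. The size is governed mainly by s and d: many early strokes must qualify on NIHSS alone, and event-time NIHSS must rarely be recorded in the medical group, before the distortion is noticeable. The formula covers only strokes that qualify on NIHSS alone. It does not model the missing reading time for the mRS criteria.

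**The case against.** The strongest reply is that assessment is event-driven in both groups. Protocol 3.9.1 has an independent site neurologist, certified in NIHSS, carry out the neurological assessment, followed by committee adjudication. Section 3.12 has the committee meet at once when an endpoint may have occurred. Neither is limited to one group. A 1-point mRS rise is also enough, and mRS is scheduled for everyone at four points after baseline, so most strokes with lasting effect are caught without NIHSS. This largely stands and is why the effect is probably small. It does not close the gap: neither section requires an NIHSS at the event or says when it is taken, and the committee can judge only the scores it receives. Section 3.8 also allows telephone visits and gives no NIHSS method for them.

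A reader might infer more than the documents support:
- **That acute NIHSS is taken only in ER patients.** Only the routine 24-72 hour and one-week examinations are ER-only. A medical patient with an in-hospital stroke has the discharge NIHSS and mRS, and 3.9.1 covers both groups. Nothing says that medical strokes are generally judged after recovery.
- **That the long period without NIHSS measures the bias.** From day 37, the latest 30-day visit, to day 365 is 365 − 37 = 328 days. The gap between the 90-day and 1-year visits is 335 − 97 = 238 to 395 − 83 = 312 days. Both are the same in the two groups. They show sparse data, not unequal ascertainment.
- **That SAE counts depend on the label.** The general SAE definition in 3.11.2 includes hospitalization, so many strokes count whether or not they are called disabling. Only the disabling-stroke part of the summary is sensitive to it.

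**Conclusion.** The point holds for early strokes and for one secondary outcome. As written, the rule gives ER patients two additional scheduled chances, in the first week after the procedure, to meet an NIHSS criterion. No fixed reading time puts the groups back on the same footing. The bias is against ER and probably small: about 1.00 to 1.19 on the risk-ratio scale under the assumed inputs, and none if event-time NIHSS is always recorded in medical patients. The disabling-stroke part of the SAE summary shares the problem. The primary outcome uses no NIHSS threshold and is unaffected.

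Two defects stand whatever the size. Table 1, 3.8 and 3.10.3 disagree on when NIHSS is taken. The pre-stroke baseline for criteria (2) and (4) is also undefined: 3.10.1 records a pre-stroke mRS separately from the enrollment mRS, and 3.9.2 does not say which score applies to a new stroke.

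**What to change.** 1. In 3.9.2, classify every adjudicated stroke in both groups from mRS read at one prespecified interval after stroke onset, by a blinded assessor. Allow a telephone reading. A death before the reading scores mRS 6 (Appendix 1), which meets criterion (1). State what happens when the reading falls after the 1-year visit.
2. If criteria (3) and (4) are kept, apply them only to an NIHSS taken at that same interval in both groups. State that the ER-only 24-72 hour and one-week routine scores do not trigger the label.
3. Define the pre-stroke baseline as the last score before that stroke.
4. In the SAP, add a sensitivity analysis using only the mRS criteria at the visits common to both groups. It uses data already scheduled, so it is possible even if follow-up has ended and fixed-interval readings can no longer be obtained.
5. Reconcile Table 1, 3.8 and 3.10.3 on NIHSS timing.

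**Cost.** Wording changes, and up to one additional mRS call per patient with a stroke. Keeping criteria (3) and (4) would also need an NIHSS examination at that interval. Some acute-severity information leaves this outcome, but it remains in the periprocedural NIHSS outcome.

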3.10 Data Collection and Management

3.10.1 Baseline clinical data collection and evaluation

When the patient is enrolled, clinical and neurological assessments will be completed per institutional standard of care. Clinical data were comprehensively collected by independent neurologists. Data to be collected and then captured on Case Report Form (CRF) include:

- ✓ Medical history, concomitant medication, demographic data collection
- ✓ Ischemic stroke history record
- ✓ Relevant concomitant medications administered
- ✓ Vital signs: Blood pressure, heart rate, respiration, body temperature
- ✓ Laboratory tests: blood routine, urine routine, blood biochemistry, coagulation function examination
 - Blood biochemistry: Renal function: creatinine, urea (or urea nitrogen), glucose, uric acid, total bilirubin, direct bilirubin, indirect bilirubin, lactate dehydrogenase, creatine kinase isoenzyme; liver function: alkaline phosphatase, glutamyl transpeptidase, aspartate aminotransferase, alanine aminotransferase; blood lipids: total cholesterol, low-density lipoprotein, high-density lipoprotein, triglyceride;
 - Coagulation function: prothrombin time (PT), activated partial thromboplastin time (APTT), thrombin time (TT), Fibrinogen (FIB), international normalized ratio (INR).
- ✓ Significant findings from clinical assessment and physical exam
- ✓ All significant neurological findings, pre-stroke mRS, mRS and NIHSS at enrollment assessed by qualified personnel at time of admission

3.10.2 Perioperative and 7-day postoperative follow-up data collection

These data include:

- ✓ Anesthesia Types: general anesthesia or local anesthesia
- ✓ Procedure times (groin puncture time, time of first microcatheter placement across the occlusion, time of initial flow restoration, time of guide catheter removal)
- ✓ Site-assessed mTICI score at post procedure
- ✓ Perioperative medication collection
- ✓ Perioperative complications
- ✓ Significant findings from clinical assessment and physical exam (e.g. all new, worsening or improved conditions)
- ✓ Patient compliance survey

3.10.3 30±7 days after enrollment data collection

- ✓ Relevant concomitant medications collection (including anti-platelet, lipid-lowering, and other medications)
- ✓ Blood pressure, blood routine, urine routine, blood biochemistry
- ✓ Fasting blood glucose, HbA1c (optional)
- ✓ Patient smoking cessation, weight, and exercise data are collected
- ✓ mRS
- ✓ The disease treatment-related cost information collection
- ✓ Outcome events observation
- ✓ Patient compliance survey

3.10.4 90±7 days after enrollment data collection

- ✓ Relevant concomitant medications collection (including anti-platelet, lipid-lowering, and other medications)
- ✓ Blood pressure, blood routine, urine routine, blood biochemistry
- ✓ Fasting blood glucose, HbA1c (optional)
- ✓ CT/MRI (optional)
- ✓ CTP/perfusion weighted imaging (PWI) (optional)
- ✓ CTA/DSA (optional)
- ✓ Patient smoking cessation, weight, and exercise data are collected
- ✓ mRS
- ✓ The disease treatment-related cost information collection
- ✓ Outcome events observation
- ✓ Patient compliance survey

3.10.5 1 year±30 days after enrollment data collection

- ✓ Relevant concomitant medications collection (including anti-platelet, lipid-lowering, and other medications)
- ✓ Blood pressure, blood routine, urine routine, blood biochemistry
- ✓ Fasting blood glucose, HbA1c (optional)
- ✓ CT/MRI (optional)
- ✓ CTP/PWI (optional)
- ✓ CTA/DSA (optional)
- ✓ Patient smoking cessation, weight, and exercise data are collected
- ✓ mRS, EQ-5D
- ✓ The disease treatment-related cost information collection
- ✓ Outcome events observation
- ✓ Patient compliance survey

3.11 Safety and Adverse Events

3.11.1 Adverse events (AE)

An adverse event (AE) is defined as any unfavorable and unintended sign, symptom, or disease that occurs to a study subject during the use of a medical treatment or intervention, regardless of whether it is deemed related to the treatment. A preexisting condition should not be reported as an adverse event unless the condition worsens or episodes increase in frequency during the adverse event reporting period.

3.11.2 Serious adverse events (SAE)

A serious adverse event (SAE) is defined as any adverse event that results in death, is life-threatening, requires hospitalization or prolongation of existing hospitalization, results in persistent or significant disability or incapacity, causes a congenital anomaly or birth defect, or requires medical intervention to prevent one of the above-mentioned outcomes.

3.11.3 Anticipated Adverse Events

Anticipated AEs are events whose nature is consistent with the safety information contained in the device documentation, specifically in the Instructions for Use (IFU) of the medical device utilized for the

study-specific procedures. The term “anticipated” does not imply that these events are expected to occur as a consequence of the underlying disease.

The assessment of whether an event is anticipated or not will be carried out by the investigator and the second assessor.

The following list of adverse events and complications (derived from the Instructions for Use, IFUs) must be considered during the assessment of “anticipatedness”. Only the events listed below are regarded as anticipated:

- Hematoma and hemorrhage at puncture site
- Perforation or dissection of the vessel
- Vasoconstriction (Vasospasm)
- Change in mental status
- Persistent neurological deficits
- Neurologic deterioration including stroke progression and stroke in new vascular territory
- Brain edema
- Ischemia
- Infection
- Allergic reactions
- Air embolism
- Intracerebral/intracranial hemorrhage
- Vascular occlusion
- Pseudo aneurysm formation
- Aneurysm perforation
- Post procedure bleeding
- Distal embolization including to a previous uninvolved territory
- Adverse reaction/anaphylaxis to antiplatelet/anticoagulation agents
- Adverse reaction (anaphylaxis, kidney damage) to contrast media
- Device(s) deformation, collapse, fracture or malfunction
- Thrombosis (acute and subacute)
- Inability to completely remove thrombus
- Arteriovenous fistula
- Seizure
- Pain/headache

3.11.4 Documentation of Adverse Events

All SAEs will be recorded in the case report form (CRF) table. The details of the SAEs, including start time, end time, duration, treatment, outcome, and relationship to the intervention, will also be documented. The frequency of SAEs will be summarized according to the study assignments. All recorded AEs and SAEs will be reported to the investigator. In this study, SAEs primarily refer to disabling strokes, symptomatic intracranial hemorrhages or death within 1 year after enrollment.

3.12 Outcome Events and Adverse Events Assessment

Endpoint events determination will be conducted through a meticulous review process by an independent Outcome Event Arbitration Committee (OEAC), guaranteeing unbiased and systematic assessment. The OEAC is constituted by three independent clinical experts, strategically selected to ensure comprehensive and objective evaluation of critical research endpoints. First two independent experts will simultaneously conduct parallel, back-to-back arbitration assessments. In cases of assessment inconsistency, a third expert will be activated to render a conclusive judgment.

Meanwhile, members of the OEAC will systematically review and independently adjudicate all reported complications in strict accordance with the predefined adverse events in the clinical events committee manual of operations. When a potential endpoint may occur, the committee board will immediately convene a meeting to evaluate whether such an event can be categorized as the primary outcome.

3.13 Blinding

All those involved in the subsequent clinical and imaging assessment of outcomes will be blinded to treatment regime.

3.14 Imaging Core Laboratory

A centralized imaging core laboratory will be utilized to provide uniform and objective assessment of radiological images. The imaging core laboratory evaluated the findings including the ASPECT (pc-ASPECTS for posterior circulation), baseline vessel imaging (CTA or DSA) for the location of the occlusion, baseline collateral circulation status evaluated by DSA (American Society of Therapeutic and Interventional Neuroradiology/Society of Interventional Radiology grade, ASTIN/SIR grade), technical efficacy outcomes regarding recanalization and residual stenosis of the qualifying artery assessed via DSA, CTA or MRA at 24-72 hours for vessel recanalization status, and the CT at 24-72 hours for the occurrence of intracerebral hemorrhage, restenosis or reocclusion during follow-up subsequent evaluation via CTA or MRA and so on. All imaging studies will undergo blinded review by experienced neuroradiological experts (over 10 years in advanced neuroimaging evaluation experience). Two neuroradiologists perform independent, masked assessments of neuroimaging studies, ensuring complete blinding to treatment allocation, clinical data, and outcomes. In cases of interpretative disagreement, a third experienced neuroradiologist will be consulted to adjudicate and provide a definitive assessment.

